12.0 Participant Information

12.1 Subject Population:

Adults aged 18-50 who meet inclusion criteria and are already scheduled to undergo venipuncture. Most will be active duty Soldiers, Family members, DA civilians, and retirees. No compensation will be provided for participating.

12.2 Age Range:

Check all the boxes that apply. If the age range of potential subjects (specimens, records) does not match the range(s) selected, please specify in the text box.

- 0-17
- 18-24
- 25-34
- 35-44
- 45-54
- 55-64
- 65-74
- 75+

18-50

12.3 Gender:

- Male
- Female
- Other

12.4 Special categories, check all that apply

- Minors /Children
- Students
- Employees - Civilian
- Employees - Contractor
- Resident/trainee
- Cadets /Midshipmen
- Active Duty Military Personnel
- Wounded Warriors
- Economically Disadvantaged Persons
- Educationally Disadvantaged Persons
- Physically Challenged (Physical challenges include visual and/or auditory impairment)
- Persons with Impaired Decisional Capacity
- Prisoners
- Pregnant Women, Fetuses, and Neonates
- Non-English Speakers
- International Research involving Foreign Nationals - Headquarters Review is necessary

12.5 Inclusion Criteria:

Order Number	Criteria
1	Adults aged 18-50
2	Currently scheduled to undergo venipuncture

12.6 Exclusion Criteria:

Order Number	Criteria
	Less than 18 years old or greater than 50 years old

1	
2	History of motion sickness (nausea or vertigo)
3	Pregnant women
4	Reported history of blood borne disease (no request will be made for which disease participant has)
5	Use of pain medication(s) on day of study
6	Current use of medical devices, including hearing aids, pacemakers, implanted cardiac defibrillators
7	Currently experiencing headache/migraine

13.0 Recruitment and Consent

13.1 Please describe the recruitment process, including how subjects will be identified and selected for the study.

When approaching the ticket stand to draw a waiting number for the lab, prospective participants will be asked by an assistant investigator located near the kiosk if they are interested in participating in the study. Participants will be selected in consecutive order (as long as the screening room is open) to avoid selection bias. However, patients who are obviously outside of the age range of 18-50 will not be asked to participate, although this process may leave room for some selection bias. If participants express desire, they will move to a screening station located in a private room near the lab to be educated on the details of the study, to include any risks. If they consent, they will fill out a screening questionnaire. If patients are eligible, they'll be given a brief tutorial on use of the VR headset and randomly assigned an envelope containing a card stating that they will use VR during venipuncture or undergo standard practice (the researcher will be blind to which group the participant is assigned to). Once instruction is complete, they'll return to the lab waiting area to draw a ticket to provide a specimen IAW standard lab practice.

13.2 Compensation for Participation:

There will not be any compensation (payment or otherwise) for participating in this study.

13.3 Please describe the pre-screening process. If no pre-screening, enter Not Applicable in the text editor

When patients approach the ticket kiosk, a member of the study team will ask them if they're interested in participating in a study related to pain control with venipuncture. To avoid perceived coercion, the recruiter will be in scrubs so that his rank will not be visible. If the participants wish to participate, they'll be directed to a screening station in a private room.

At the screening station, candidates will be screened to insure they meet inclusion/exclusion criteria by completing a prescreening form that addresses all participation criteria. After that, they'll be provided informed consent documents and will undergo a brief tutorial for use of the VR headset prior to returning to the lab waiting area to draw a ticket.

13.4 Consent Process:

Revised Common Rule, Section 219.116: General requirements for informed consent, whether written or oral, are set forth in this paragraph and apply to consent obtained in accordance with the requirements set forth in paragraphs (b) through (d) of this section. Broad consent may be obtained in lieu of informed consent obtained in accordance with paragraphs (b) and (c) of this

section only with respect to the storage, maintenance, and secondary research uses of identifiable private information and identifiable biospecimens.

Are you requesting a waiver or alteration of informed consent?

Yes No

Please explain the consent process:

The consent process will take place at the time of recruitment, and will occur in a private room with only the subject and investigator present. Participants will be walked through the informed consent document section by section, being allowed time to read each section and decide if they would like to continue. Participants will be informed prior to starting that participation is voluntary and that they may choose not to participate at any time during the consent process, throughout the duration of the study, and after it is complete. They will be informed on the process to withdraw from the study which will be to contact [name] at the above listed email or phone number which will be on the consent form and pointed out to the participant. Once complete the participant will be asked to sign the consent document and the PI will sign the consent form. Copies of the signed consent form will be made and provided to the participant. Participants will also be asked to fill out the Self-reported participant data form for inclusion /exclusion from the study and will be informed prior to leaving whether they are eligible to participate. All questions will be answered by the PI or AI at any point during participant contact or via email or phone.

13.5 DoDI 3216.02 requires an ombudsman to be present during recruitment briefings when research involves greater than minimal risk and recruitment of Service members occurs in a group setting. If applicable, you may nominate an individual to serve as the ombudsman.

N/A
 Propose ombudsman

13.6 Withdrawal from Study Participation:

Explain the process for withdrawal and specify whether or not the subjects will be given the opportunity to withdraw their data their data/specimens in the event they wish to withdraw from the study

The decision to participate in this study is completely voluntary. No one will be coerced or intimidated into participating in this project. The principal investigator or his associate investigator will adequately answer any and all questions about this study, participation, and the procedures involved. If significant new findings develop during the course of this study that may relate to participant participation, they will be informed.

Subjects may withdraw this consent at any time and discontinue further participation in this study without affecting eligibility for care or any other benefits to which they are entitled. Should participants choose to withdraw, they must simply inform [name] that they have no desire to continue during their visit at the lab. As no PHI will be collected and subjects will be unidentifiable after completing questionnaires, participants will be unable to withdraw after completing all questionnaires.

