Once approved for participation in the study all participants will undergo a brief instructional class on how to operate the HMD and will be allowed sufficient time to become comfortable with its use. We expect approximately 5-10 minutes to be required for this portion of the study. Once familiar with the use of the VR headset, participants will be asked to randomly draw an envelope from a container. This envelope will contain a block and sequence number. The block and sequence number will be the subject ID and will correspond to a predetermined number set on a separate document that will determine if the participant will use the HMD during venipuncture or not. The screener will not have immediate access to the list showing which group the participant will be assigned to. One member of the study team will be present in the lab room to ensure the participant uses the VR headset (or not) according to what is randomly drawn. This member of the research team will have the list showing whether or not the participant is assigned to the control arm or the experimental arm. The participants will then proceed to the specimen room to undergo venipuncture.

Venipuncture for both groups will occur in the non-dominant arm. The reasoning for this is that the Oculus Go requires one free hand to use a controller. This will ensure that the individuals participating are able to effectively use the device. Those unable to undergo venipuncture in the non-

dominant arm will undergo venipuncture in the dominant arm instead and will use the Oculus Go controller with their non-dominant hand.

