11.5 Please provide a justification for your sample size

A study performed by Todd et al 1995 and a later validation study by Gallagher et al 2001 both found that a minimum clinically significant change in pain as measured on the VAS is 13mm. Both studies found that the change in pain reported as "a little more pain" or "a little less pain" after intervention averaged to 13mm. Both studies also found that the standard deviation of change in pain reported on the VAS as "a little more pain" or "a little less pain" was 17mm.

Since the t-test will be used at the end of the study to determine if the effects are statistically significant, the E/S ratio (expected effect size divided by the standard deviation of the outcome variable) was used to determine the sample size. The E/S ratio is being estimated based on the studies cited above. The expected effect size (13mm) divided by the standard deviation (17mm) =0.76. To ensure a 2-sided α 0.05 and β 0.20, a minimum of 27 subjects are required for each arm. This is based on a sample size calculator created by Dhand et al as well as appendix 6A of *Designing Clinical Research* authored by Hulley et al.

Although a total of only 54 participants is required for this study to be effectively powered, we're requesting 60 to account for a potential dropout rate of 10%.

Minitab software will be utilized for final data analysis.

11.6 Data Analysis Plan: Complete description: Background, Objectives, Design, Step by Step how the project is going to be done, Data analysis plan:

The primary outcome be measured as the average pain rating between the two groups as measured on the VAS. The t-test will be used to compare the two groups to determine if the difference is statistically significant. The difference between the two groups should be at least 13mm to be considered clinically significant.

The preprocedural anxiety will also be measured using the VAS and the average difference will be reported in the data, although a minimum clinically significant score is not available.

Since participants will be randomly assigned to each study arm, it will be impossible to insure an even spread of ages between the two study arms. It may be possible that pain perception changes with age, and since this study will include ages 18-50, data tables comparing the average changes between those in different age groups (i.e. 18-25, 26-33, 34-41, 42-50). A separate subgroup analysis will be performed comparing different age subgroups.

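### Sections 10.1 and 13.1 give incompatible allocation procedures (a coded envelope versus a card naming the arm), and the container draw in 10.1 does not follow the block sequence

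*Combined protocol and SAP*

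**What the plan says.** **Section 10.1 (Study Procedures).** After the headset tutorial, "participants will be asked to randomly draw an envelope from a container". On the contents: "This envelope will contain a block and sequence number". On the link to the arm: "The block and sequence number will be the subject ID and will correspond to a predetermined number set on a separate document". On access: "The screener will not have immediate access to the list showing which group the participant will be assigned to". The list sits with a team member in the lab room: "This member of the research team will have the list showing whether or not the participant is assigned to the control arm" or to the experimental arm.

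**Section 13.1 (recruitment process).** After the tutorial the participant is "randomly assigned an envelope containing a card stating that they will use VR during venipuncture or undergo standard practice". The same sentence adds in parentheses that "the researcher will be blind to which group the participant is assigned to". The participant then goes back to the waiting area to take a lab ticket.

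The documents do not state whether envelopes are sealed or opaque, who opens them, where and when, the block size, how the list is generated, whether there is one container or one per block, or which researcher is blind.

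**The concern.** The two sections differ on what an opened envelope reveals. Staff working from 13.1 would prepare different envelopes from staff working from 10.1, and only the 10.1 envelope keeps the arm hidden once opened.

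This matters because of the following features of the trial:

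- Pain and anxiety are marks the participant makes on a visual analogue scale. Knowing the arm while waiting could change what the participant expects and so what is reported.
- Everyone tries the headset before allocation (10.1), and controls then wear it switched off. A participant who learns of assignment to the control arm could lose interest.
- Withdrawal is allowed during the lab visit (13.6). Someone who leaves before venipuncture has no pain score. Section 11.1 includes all enrolled subjects in the analysis but gives no method for missing outcomes.

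The second issue is separate. Section 10.1 refers to blocks and sequence numbers, which have a purpose only if envelopes are used in order. A random draw does not use them in order.

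**Working it through.** **1. The two procedures side by side**

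| Feature | 10.1 | 13.1 |
|---|---|---|
| How obtained | Participant draws from a container | Randomly assigned; no container mentioned |
| Contents | Block and sequence code | Card naming the arm |
| Link to arm | Separate list in the lab room | None needed |
| Safeguard | Screener lacks immediate access to the list | Researcher said to be blind; who and how not given |
| Timing | After tutorial, before the specimen room | With the tutorial, before return to the waiting area |

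The blinding statement in 13.1 can be squared with the card if the participant opens a sealed envelope out of the researcher's sight. Even then the participant would know the arm. Under 10.1 neither the participant nor the screener can read the arm from the envelope.

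**2. The plan's sample size.** Section 11.5 states: "To ensure a 2-sided α 0.05 and β 0.20, a minimum of 27 subjects are required for each arm". With a difference of 13 mm and SD 17 mm:

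n = 2 × (1.960 + 0.842)² × (17/13)² = 2 × 7.851 × 1.710 = 26.8, so 27 per arm; and 54 / (1 − 0.10) = 60.

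The figure reproduces (the exact t-test gives 27.8, so 28). Nothing in this point changes it.

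**3. Balance with a random draw.** Assumptions: one container of 60 envelopes, 30 per arm (11.4), not returned after use, since each code becomes a subject ID. The number of VR envelopes among the first m draws is hypergeometric, and the SD of the arm difference is √[m(60 − m)/59].

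- m = 20: data collection is expected to take 3-4 days (16.1), so 60/4 = 15 to 60/3 = 20 participants a day. SD = √(800/59) = 3.7. The chance of 13:7 or worse is 17.0%. With blocks of 4 used in order (assumed size) it is zero, because 20 is five complete blocks.
- m = 30: SD = √(900/59) = 3.9. The chance of 18:12 or worse is 19.6%.
- m = 54: a deviation of 3 or more from 27:27 requires the six unused envelopes all to be from one arm: 2 × C(30,6)/C(60,6) = 2 × 593,775 / 50,063,860 = 2.4%. This is also the largest imbalance possible at that point.
- m = 60: exactly 30:30.

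Over 5,000 simulated sequences, the mean maximum running imbalance was 6.2 with one container, against 2.0 with blocks of 4 and 2.7 with blocks of 6.

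**4. Effect on power (exact t-test).** 78.7% at 27:27 and 78.2% at 24:30. The cost is negligible.

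**5. Predictability.** Someone who knows all past assignments and always guesses the arm that is behind is right about 57% of the time with one container, 71% with blocks of 4 and 68% with blocks of 6. The container draw is the less predictable method.

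**6. Sensitivity to arm-related exit (illustration only).** The documents give no rate. Suppose 1 to 3 of 30 controls leave on learning their arm and their pain would have differed from that of the stayers by 10 to 30 mm. The control mean shifts by (number leaving/30) × difference: from (1/30) × 10 = 0.3 mm to (3/30) × 30 = 3.0 mm, the latter being 3.0/13 = 23% of the 13 mm target. Neither the rate nor the gap has a source in the documents.

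**The case against.** The strongest reply is that concealment is not shown to be broken. Section 13.1 says the researcher will be blind, and 10.1 keeps the list from the screener. In both sections assignment follows consent and eligibility, and expected pain and anxiety are recorded on the screening questionnaire, so entry and those baselines are not exposed to a known arm. The documents nowhere say that the card is opened at the screening station. All of this stands. It makes concealment unclear rather than absent, and it does not remove the contradiction over what the envelope holds.

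A reader might infer several stronger things that the documents do not support:

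- **That both sections use a container.** Only 10.1 does, so the blocking point applies to 10.1 alone.
- **That an unwelcome assignment could be put back and redrawn unseen.** This joins the card of 13.1 to the container of 10.1. Under 10.1 nobody at screening can tell a welcome code from an unwelcome one, and the code is the subject ID on a predetermined list.
- **That random drawing weakens concealment.** Step 5 shows the opposite. Any concealment problem comes from the arm-naming card and the unstated details of opening and blinding.
- **That power or final balance suffers.** Step 4 shows a negligible power cost, and a balanced list used in full ends at 30:30. An uneven split early on matters only if outcomes drift over the 3-4 days, and the documents give no reason to expect that.

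**Conclusion.** The contradiction is real and lies in current text: 10.1 and 13.1 cannot both be followed. If 13.1 is used, the participant, and possibly screening staff, could know the arm before venipuncture, which could affect anticipation or withdrawal. The size of that effect is unknown. The 0.3 to 3.0 mm range shows only how sensitive the control mean would be under assumed exits; it is not an estimate.

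As written, 10.1 also does not deliver the blocking it names, unless each block has its own container. The cost is limited to balance over time (17% chance of 13:7 or worse at 20 draws, 2.4% chance of the extreme split at 54) and to the lack of an ordered sequence against which a skipped number would show. These figures rest on one balanced container of 60 drawn without replacement. The point should be fixed before recruitment because doing so costs almost nothing, not because harm has been demonstrated.

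**What to change.** Write one procedure and use it in both 10.1 and 13.1:

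- Keep the code-only envelope of 10.1 and delete the arm-naming card from 13.1.
- Use sealed, opaque, sequentially numbered envelopes, issued in list order and not drawn from a container.
- Have the lab-room member, who takes no part in screening or enrolment, reveal the arm only when the participant is seated for venipuncture, and log each number as used.
- State how the list is generated, who opens the envelope and who is blind. Keep the block size from recruiting staff.

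The cost is a wording change and a simple log, with the same staff and envelopes. Late disclosure fits the existing set-up, since 10.1 already has both arms wear a headset. The sample size is unchanged.

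There is one downside. Small blocks issued in order are somewhat more predictable than a single container to anyone who knows past assignments (about 71% against 57% for blocks of 4), so the list and the record of past assignments must stay away from screening staff.

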14.0 Risks and Benefits

14.1 Risks of Harm:

Identify all research-related risks of harm to which the subject will be exposed for each research procedure or intervention as a result of participation in this study. Consider the risks of breach of confidentiality, psychological, legal, social, and economic risks as well as physical risks. Do not describe risks from standard care procedures; only describe risks from procedures done for research purposes

Risk associated with this study may include dizziness, loss of awareness, eye strain, temporary visual abnormalities (including blurred or double-vision), muscle-twitching, impairment of hand-eye coordination, impaired balance, excessive sweating, drowsiness, fatigue, headache, lightheadedness, disorientation, nausea and/or vomiting from the use of the VR device, although the frequency of these events is rare not well-defined. Approximately 1 in 4,000 users may experience seizures despite having no history of seizure disorders; seizures are more common in children (who are excluded from this study). Risk of experiencing adverse events may be increased if patients have a history of seizure disorders, or if they have other underlying neurological disorders. Risk may also be increased if with the use of certain medications, although this data has not been studied.

There is also risk associated with accidental movement of arm during venipuncture, which could result in mistakenly puncturing unintended an area of the patients skin. However, this is unlikely as standard practice when drawing blood is for the phlebotomist to steady the patient's arm and draw skin taught with the hand not holding the needle, minimizing the likelihood that the patient will move.

There is also a risk in loss of subject confidentiality, which is addressed in section 14.2.

14.2

Measures to Minimize Risks of Harm (Precautions, safeguards):

For each research procedure or intervention, describe all measures to minimize and/or eliminate risk of harms to subjects and study personnel

Risks associated with the use of VR will be mitigated by screening for and excluding patients with a recent history of vertigo or dizziness, motion sickness, current symptoms of nausea and/or vomiting, and pregnancy. Additionally, in an effort to minimize risk, the following instructions will be provided during the tutorial:

- If you begin to experience nausea, headache, eye strain, or any other discomfort, please remove the headset and inform a member of the research team immediately

Participants will also be advised to request breaks as needed if they experience uncontrollable anxiety, or they may withdraw if they request as stated in the consent form.

To minimize the risk of patients moving arms during venipuncture, phlebotomists will be asked to alert the patient that they are about to penetrate the skin and to hold still.

To minimize the risk of loss of confidentiality, all information collected will be controlled with strict record keeping procedures. All de-identified data collected will be stored in a locked drawer behind a locked door when not in use and only accessible to the research team members. Once gathered, the data will be transferred into electronic form on a secure CAC-enabled/password protected government computer that will be in the possession of the PI, when not in the PI's possession it will be stored in a locked room. The electronic documents will be kept for 3 years and then deleted. There will be no legal or economic risks associated with this study. No adverse action will be taken against anyone who withdrawals from the study at any time.

14.3

Confidentiality Protections (for research records, data and/or specimens):

Describe in detail the plan to maintain confidentiality of the research data, specimens, and records throughout the study and at its conclusion (e.g., destruction, long term storage, or banking). Explain the plan for securing the data (e.g., use of passwords, encryption, secure servers, firewalls, and other appropriate methods). If data will be shared electronically with other team members/collaborators outside the institution, describe the method of transmission and safeguards to maintain confidentiality. Explain whether this study may collect information that State or Federal law requires to be reported to other officials or ethically requires action, e.g., child or spouse abuse

All de-identified data collected will be stored in a locked drawer behind a locked door when not in use and only accessible to the research team members. Once gathered, the data will be transferred into electronic form on a secure CAC-enabled/password protected government computer that will be in the

possession of the PI. When not in the PI's possession it will be secured in a locked office. The de-identified electronic data will be stored on the attached Excel spreadsheet. Paper copies will be shredded once data has been transferred. Once the study is complete the electronic documents will be maintained on the primary investigator's CAC-enabled/password protected government computer until the computer is turned in upon PCSing and then deleted.

14.4 Potential Benefits:

Describe any real and potential benefits of the research to the subject and any potential benefits to a specific community or society

If the individuals in the research are considered experimental subjects (per 10 USC 980), and they cannot provide their own consent, the protocol must describe the intent to directly benefit all subjects

The subjects in the experimental group will potentially benefit from this study via reduction in anxiety and pain control, but will not directly benefit from this study in any other way. If Virtual Reality is shown to decrease pain intensity and anxiety levels with venipuncture, it may be offered in the lab setting, clinic setting, emergency room setting, or deployed setting to improve the care that can be provided.

14.5 Privacy for Subjects:

Describe the measures to protect subject's privacy during recruitment, the consent process, and all research activities, etc.

During the screening process no PHI will be collected. The participant's name and signature will be on the consent form, but will not be linked to any PHI. The screening questionnaire will contain age and gender, and will ask several questions about health, but will not be linked to the consent form and therefore will not contain PHI. This will be performed in a private room with only the member of the study team collecting the data present. Once gathered, the data will be stored in electronic form on a secure CAC-enabled/password protected government computer that will be in the possession of the PI. After paper documents are transferred electronically they will be shredded, the electronic documents will be kept for 3 years and then deleted.

14.6 Incidental or Unexpected Findings:

Describe the plan to address incidental findings and unexpected findings about individuals from screening to the end of the subject's participation in the research. In cases where the subject could possibly benefit medically or otherwise from the information, state whether or not the results of screening, research participation, research tests, etc., will be shared with subjects or their primary care provider. State whether the researcher is obligated or mandated to report results to appropriate military or civilian authorities and explain the potential impact on the subject

Incidental findings are unlikely given the procedures in this study. However, should one arise and the subject could possibly benefit from the information, they will be informed.

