---------------------	----------------	---------------	------------------	-----------------------

How likely would you be to request Virtual Reality if it were available for use for other painful or anxiety-inducing procedures?

5 Very Likely	4 Likely	3 Not Sure	2 Unlikely	1 Very Unlikely
------------------	-------------	---------------	---------------	--------------------

10.2 Data Collection:

Describe all the data variables, information to be collected, the source of the data, and how the data will be operationally measured.

The independent variable for this study is the use of VR or lack thereof. The dependent variables include accurately measuring anxiety levels pre and post procedure, pain levels after the procedure, and satisfaction with the procedure in regards to pain control, anxiety management, and ease of use. The participant's gender, age, and a minimal medical history will be obtained for purposes of inclusion or exclusion from the study. The information collected relevant to the conduct of the study will include any history of bloodborne disease, anxiety, seizures, pregnancy status, right vs left handedness, VR experience, nausea, vomiting, or vertigo. Participants will also be asked to rate their expected pain and anxiety associated with venipuncture using the Visual Analog Scale (VAS). The above information will be collected on the self-reported data sheet prior to providing specimens. The questionnaires will also enquire as to whether the participant took any pain medications prior to arrival, as well as rate pre and post-procedure anxiety level on a VAS scale. Finally, patients will then rate their procedure related pain intensity on the VAS scale.

Participants will also be asked about their satisfaction level with the use of VR in regards to pain control, anxiety management, and ease of use and their likelihood of requesting VR if available in the future using the Likert scale. All information will be provided and data collected voluntarily, and participants may choose not to answer any questions they choose.

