The only known unanticipated problem involving risk to subject or others (UPIRSO) is seizure. As stated in the Oculus Go user manual, this has an incidence of approximately 1 in 4,000 users, although it most commonly occurs in children (who are excluded from the study). In the event that this occurs, subjects will have all sharp objects moved away from them, be placed laterally on their sides, and emergency personnel will be contacted for transport to the ER for further evaluation and treatment.

Unanticipated problems involving risk to subjects or others will be reported promptly providing initial notification of the event as quickly as possible after the research team's knowledge of the event, but within (5) business days of identification by [contact]), by e-mail ([contact]), or by [contact]) to the Office of the Regional Health Command Central (RHC-C) Institutional Review Board (IRB). A complete written report will follow the initial notification within ten (10) business days. The complete report will be sent to the RHC-C IRB Office I, Brooke Army Medical Center, ATTN: MCHE-ZQ, Department of Quality and Safety, [name].

To fulfill the local responsibility for monitoring and oversight of research, all potential UADEs that are unexpected and determined to be at least possibly related or definitely related to research participation

will be promptly reported within 24 hours of learning of the event by telephone or by email to the local IRB Office. A complete report will follow the initial notification within 5 business days.

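### Seizure history is collected and named as a risk factor, but no exclusion covers it, so a person with a seizure disorder is eligible to use the headset

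*Combined protocol and SAP*

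**What the plan says.** Section 14.1 gives a base rate, "Approximately 1 in 4,000 users may experience seizures despite having no history of seizure disorders", and then identifies who may be at higher risk: "Risk of experiencing adverse events may be increased if patients have a history of seizure disorders, or if they have other underlying neurological disorders".

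Section 10.2 says that "a minimal medical history will be obtained for purposes of inclusion or exclusion from the study". Its next sentence lists the information to be collected, beginning with "any history of bloodborne disease, anxiety, seizures, pregnancy status". Section 13.4 describes the self-report form as serving eligibility and says participants learn from the team whether they qualify.

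The inclusion criteria in 12.5 are age 18-50 and a scheduled venipuncture. The seven exclusions in 12.6 concern age, motion sickness, pregnancy, blood-borne disease, pain medication on the day, medical devices, and a current headache or migraine. Section 14.2 says VR risk will be reduced by screening for and "excluding patients with a recent history of vertigo or dizziness, motion sickness, current symptoms of nausea and/or vomiting, and pregnancy". Section 13.3 says candidates are screened by "completing a prescreening form that addresses all participation criteria".

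Section 16.1 names seizure as the only known unanticipated problem involving risk. It sets out how to care for a participant who has one and how to report it.

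**The concern.** The risk section identifies a higher-risk group and the data section collects the item that identifies it, but the eligibility rules do not use that item. Followed as written, the plan lets a person with a known seizure disorder meet 12.5, pass 12.6 and 14.2, and be given active VR. The only exclusion that the plan links to seizure is that of children (14.1 and 16.1). The adult group named in 14.1 is left in.

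Both arms are affected. Under 10.1 every participant is taught to operate the headset, over roughly 5-10 minutes, before drawing an envelope. Control participants wear a switched-off headset only later, during the draw.

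The remaining safeguards act too late or depend on the participant. Section 14.2 tells participants to take the headset off if they feel discomfort, which someone having a seizure may be unable to do. Section 16.1 applies after the event. In the VR arm the device is also in use while a needle is in the arm.

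**Working it through.** **Text check.** Each place where seizure history could be handled was compared:

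| Section | Seizure history |
|---|---|
| 10.2 Data collection | Collected |
| 14.1 Risks | Named as possibly raising risk |
| 12.5 Inclusion | Not mentioned |
| 12.6 Exclusion, items 1-7 | Not mentioned |
| 14.2 Screening safeguard | Not mentioned |
| 13.3 Prescreening form | Form not shown; described as covering the participation criteria, which do not include it |
| 16.1 Reportable events | Response and reporting only |

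No other section excludes these people. Sections 13.1 and 13.3 order consent and screening differently, but both place eligibility before the tutorial, so an exclusion would take effect before any exposure.

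**Size.** The plan states no figure to reproduce on this point. From the documents: n = 60 (11.2) and base seizure rate r = 1/4,000 (14.1). Assumed, because the documents give neither: prevalence p of seizure history (0.5%, 1%, 3%) and risk multiplier k for those with it (2, 10, 50). The base rate is stated per user with no duration. It is applied to all 60 because all use the headset in the tutorial.

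For context, at the base rate alone the chance of at least one seizure among 60 users is 1 − (1 − 1/4,000)^60 = 1.5%.

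How often the case arises:

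| p | Expected with history, 60p | Chance of at least one, 1 − (1 − p)^60 | Screened to enrol 60, 60/(1 − p) |
|---|---|---|---|
| 0.5% | 0.3 | 26.0% | 60.3 |
| 1% | 0.6 | 45.3% | 60.6 |
| 3% | 1.8 | 83.9% | 61.9 |

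What exclusion changes, if each such person is replaced by one without the history:

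| p, k | Individual risk, k·r | Seizures avoided, 60p(k − 1)r | Share of expected seizures, pk/(pk + 1 − p) |
|---|---|---|---|
| 0.5%, 2 | 1 in 2,000 | 0.000075 | 1.0% |
| 1%, 10 | 1 in 400 | 0.00135 | 9.2% |
| 3%, 50 | 1 in 80 | 0.02205 | 60.7% |

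Worked middle case: 60 × 0.01 × 9 / 4,000 = 0.00135 seizures avoided, and 0.1 / (0.1 + 0.99) = 9.2% of expected seizures arising in 1% of participants.

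The individual risk and the seizures avoided scale directly with r. The share and the chance of enrolling at least one such person do not depend on r.

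**The case against.** Several counter-arguments have some force.

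- **The list in 10.2 does not prove intent to exclude.** Seizures sit beside handedness and VR experience, which are not exclusions. This is correct, and 10.2 does not say item by item which answers decide eligibility. The concern does not need that reading, because 14.1 independently names seizure history as a risk factor.
- **The screening form is not visible and may stop such a person.** That cannot be ruled out. But the form is described only by reference to the participation criteria, so any such stop would have no basis in the visible text.
- **12.6 is not the complete screening list, since 14.2 adds current nausea and vomiting.** True, but seizure history is on neither list.
- **The magnitude rests on assumptions.** It does, and the seizures avoided span about 290-fold. Section 14.1 speaks of adverse events in general, so applying k to the seizure rate is a further assumption. Sections 14.1 and 16.1 also say seizures are more common in children. If 1 in 4,000 covers all ages, the adult base rate is lower, and the individual risks and seizures avoided above are too high.
- **Participants are informed and supervised.** Consent covers the risks, a team member is in the lab room, and a seizure response is specified. These measures make the exposure informed and watched but do not prevent it.
- **Other flagged groups remain.** Section 14.1 also mentions other neurological disorders and certain medications. This point covers only seizure history, the flagged item that 10.2 lists for collection.

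**Conclusion.** The concern holds. The gap in the text is certain: the plan records seizure history, says it may raise risk, and has no visible rule that acts on it. A person with a known seizure disorder is eligible and will use the headset whichever arm is drawn.

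The numbers are much less certain. The expected benefit in seizures avoided is a small fraction of one event over the whole assumed range. The chance that the screener meets at least one such person is not small, at roughly one in four even at 0.5% prevalence. The reasons to act are protection of an identifiable person and a clear screening rule; a large expected reduction in events is not among them. Randomisation, the primary analysis and the power are untouched. This is a change the team should make.

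**What to change.** Add an eighth exclusion to 12.6: *Any self-reported history of seizure or seizure disorder*. Put the same words in the 14.2 screening list, and have a positive answer to the seizure item stop enrolment before the headset tutorial. If the team means to admit these people, it should say so in 12.6 and 14.1 and give the reason.

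The cost is one criterion and one phrase, since the information is already collected. About 0.3 to 1.9 more people would need screening to enrol 60 (60.3 − 60 to 61.9 − 60). Because exclusion precedes allocation, the 30 per arm stand. Results would no longer extend to people with a seizure history, who make up at most 3% of candidates under the assumed range.
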